#### **6.1.3. General Considerations for Analyses during the Post-Treatment Follow-Up Period (Period 3)**

For the safety analyses during Period 3, baseline is defined as the last nonmissing assessment on or prior to entering Period 3, that is, on or prior to Week 52 (Visit 15), or ETV.

Safety data collected will be summarized using descriptive statistics.

## 6.2. Adjustments for Covariates

The randomization to treatment groups in Period 2 is stratified by country and screening MRI/CRP status (that is, positive MRI and elevated CRP; positive MRI and nonelevated CRP; negative MRI and elevated CRP; elevated CRP is defined as >5.00 mg/L) as described in Protocol Section 6.2. The countries will be categorized into geographic regions for statistical analysis (Table RHBX.6.3). Unless otherwise specified, the statistical analysis models will adjust for geographic region and screening MRI/CRP status (that is, positive MRI and elevated CRP; positive MRI and nonelevated CRP; negative MRI and elevated CRP; positive MRI is defined as presence of sacroiliitis on MRI based on central reading; elevated CRP is defined as >5.00 mg/L at screening visit (Visit 1).

Table RHBX.6.3 outlines the country allocations and classifications for geographic regions.

**Table RHBX.6.3. Geographic Regions for Statistical Analysis**

Geographic Region	Countries
Europe	Austria, Russia a , Czech Republic, Finland, Poland, Germany, Romania, The Netherlands
non-Europe	United States, Canada, Argentina, Brazil, Mexico, Japan, Korea

a Russia is combined with European countries due to the preponderance of investigative sites in the western part of Russia.

In general, when an MMRM is to be used for analyses, baseline value and baseline-by-visit interactions will be included as covariates; when an ANCOVA is to be used for analyses, baseline value will be included as a covariate.

## 6.3. Handling of Dropouts or Missing Data

In accordance with precedent set with other Phase 3 axSpA trials (van der Heijde et al. 2006; Inman et al. 2008), the following methods for imputation of missing data will be used.

### 6.3.1. Nonresponder Imputation

Analysis of categorical efficacy and health outcome variables will be assessed using a nonresponder imputation (NRI) method. Patients will be considered nonresponders for the NRI analysis if they do not meet the clinical response criteria or have missing clinical response data at the primary analysis time points. All nonresponders at Week 16 (Visit 8), as well as all patients who discontinue study treatment at any time prior to Week 16 for any reason, will be defined as nonresponders for the NRI analysis at Week 16. Similarly, all nonresponders at Week 52 (Visit 15), as well as patients who discontinue study treatment at any time prior to Week 52 for any reason, will be defined as nonresponders for the NRI analysis at Week 52. Patients who are deemed as inadequate responders by the investigator on or after Week 16 but remain on initially assigned blinded study treatment and only have modifications in concomitant medications will not influence whether or not a patient would be considered a nonresponder. Patients who stopped originally assigned blinded study treatment and use rescue ixekizumab 80 mg Q2W will be analyzed as nonresponders for the Week 52 analysis. They will be considered as nonresponders after the time of initiation of biologic rescue of ixekizumab 80 mg Q2W.

Randomized patients without at least 1 postbaseline observation will also be defined as nonresponders for the NRI analysis.

The NRI may be applied at any time point specified for analysis.

### **6.3.2. Modified Baseline Observation Carried Forward**

An mBOCF analysis will be performed on continuous efficacy and health outcomes variables in the major and other secondary objectives. For ITT population, if patients did not initiate the rescue ixekizumab 80 mg Q2W and discontinue study drug due to an AE, the baseline observation will be carried forward to the corresponding time point for evaluation; if they discontinue study drug for any other reason, the last nonmissing observation before study drug discontinuation will be carried forward to the corresponding time point for evaluation. For ITT patients who discontinue originally assigned blinded study treatment and initiate biologic rescue of ixekizumab 80 mg Q2W (inadequate responders), the last nonmissing observations prior to the initiation of rescue ixekizumab 80 mg Q2W will be carried forward to subsequent time points. Randomized patients without at least 1 postbaseline observation will not be included for evaluation with the exception of patients discontinuing study treatment because of an AE.

For IR population during the biologic rescue of ixekizumab period, if patients discontinue study drug due to an AE, the baseline observation at Week 0 will be carried forward to subsequent time points; if they discontinue study drug for any other reason, the last nonmissing observation will be carried forward to the corresponding time point for evaluation.

### **6.3.3. Last Observation Carried Forward**

No last observation carried forward (LOCF) analysis will be performed.

### **6.3.4. Placebo Multiple Imputation**

For the primary endpoint ASAS40 and major secondary endpoint change from baseline in ASDAS, if randomized patients were treated with biologic rescue of ixekizumab 80 mg Q2W (inadequate responders), all observations after the time of initiation of biologic rescue of ixekizumab will be set as missing. The placebo multiple imputation (pMI) method will be used for the analyses of ASAS40, and ASDAS change from baseline at Week 16 (Visit 8) and Week 52 (Visit 15) for missing data due to rescue and due to discontinuations. [Appendix 1](#) presents the detailed scientific justification of the pMI method.

Placebo multiple imputation assumes that the statistical behavior of drug- and placebo-treated patients after discontinuing study medication or rescue by ixekizumab 80 mg Q2W becomes that of placebo-treated patients. Multiple imputations (MIs) are used to replace missing outcomes for drug- and placebo-treated patients, utilizing multiple draws from the posterior predictive distribution estimated from the placebo arm.

Data are processed sequentially by repeatedly calling SAS® PROC MI to impute missing outcomes at visits  $t=1, \dots, T$ .

1. *Initialization.* Set  $t=0$  (baseline visit).

2. *Iteration.* Set  $t=t+1$ . Create a dataset combining records from drug- and placebo-treated patients with columns for covariates  $\mathbf{X}$  and outcomes at visits 1,...,t with outcomes for all drug-treated patients set to missing at visit t and set to observed or imputed values at visits 1,...,t-1.
3. *Imputation.* Run Bayesian regression in SAS® PROC MI on this data to impute missing values for visit t using previous outcomes for visits 1 to t-1 and baseline covariates. Note that only placebo data will be used to estimate the imputation model since no outcome is available for drug-treated patients at visit t.
4. Replace imputed data for all drug-treated patients at visit t with their observed values, whenever available. If  $t < T$  then go to Step 2, otherwise proceed to Step 5. Repeat Steps 1 to 4  $m$  times with different seed values to create  $m$  imputed complete datasets.
5. *Analysis.* For each completed dataset, use the model as would have been applied had the data been completed for the outcome. For ASAS40, the missing binary outcomes will be imputed directly for each patient before fitting into the analysis model. A logistic regression model will be applied.

The final inference on treatment difference is conducted from the multiple datasets using Rubin's combining rules, as implemented in SAS® PROC MI ANALYZE.

Thus, in the effectiveness context, pMI assumes no pharmacological benefit of the drug after dropout but is a more reasonable approach than mBOCF and NRI because, unlike mBOCF and NRI, pMI accounts for uncertainty of imputation, and therefore does not underestimate standard errors, and limits bias by taking into account study/placebo effects. In the efficacy context, pMI is a specific form of a missing-not-at-random (MNAR) analysis expected to yield a conservative estimate of efficacy.

### **6.3.5. Tipping Point Analyses**

For the primary endpoint ASAS40 and major secondary endpoint change from baseline in ASDAS, if randomized patients were treated with biologic rescue of ixekizumab 80mg Q2W (inadequate responders), all observations after the time of initiation of biologic rescue of ixekizumab will be set as missing.

To evaluate the robustness of statistical analyses of key efficacy data and assumptions inherent in missing data imputation methods, tipping point analyses will be used for the missing data of ASAS40 as well as mean change from baseline in ASDAS at Weeks 16 and 52 due to rescue and due to discontinuations. [Appendix 2](#) presents the detailed scientific justification of the tipping point method.

For continuous variables (mean change in ASDAS at Weeks 16 and 52), a 2-step MI method is used to impute missing data independently by treatment group:

1. The first step is to create a monotone missing pattern using a Markov chain Monte Carlo method (using SAS® Proc MI with MCMC option) to handle intermittent missing data.
2. The second step is to use a set of Bayesian regressions (using Proc MI with MONOTONE option, 20 imputed data sets) for the imputation of monotone dropouts.

The regression models are fit sequentially starting from the first visit with at least 1 missing response using treatment as a fixed effect and values (observed or imputed) from the previous visits as covariates. All patients in the ITT Population with a baseline value are included in the analyses, and all observed data on and prior to the time of rescue are utilized from each patient. A delta score is added to all imputed scores (at the primary time point) for patients in any ixekizumab treatment group in order to evaluate a scenario in which patients treated with ixekizumab would have worse outcomes than patients from the placebo group. An independent delta score will be added to placebo group and is capped for individual patients based on the range of the outcome measure being analyzed. The delta score will not be added to the observed values.

Analyses using the principal analysis model are aggregated across the  $m$  imputed data sets using SAS® PROC MI ANALYZE in order to compute a p-value for the treatment comparison for a given value of the delta score.

Sensitivity of the analysis conclusion to the choice of delta score is determined by repeating the aforementioned MI steps and analyses by gradually increasing the delta score, thus evaluating scenarios with increasingly worse imputed values for missing data for patients treated with ixekizumab. The tipping point is identified as the delta score value which leads to a loss of statistical significance when evaluating ixekizumab relative to the placebo group.

The tipping point analysis will be used for categorical data (ASAS40 at Weeks 16 and 52) in a similar fashion:

- For ixekizumab groups, a range of response probability (for example, probability = 0, 0.1, 0.2, ..., respectively) will be used to impute the missing values for ASAS40 (each probability is imputed based on 20 data sets). NRI will be used as the most extreme case.
- For the placebo group, different response probability (for example, probability = 0, 0.2, ..., 1, respectively) will be used to impute the missing values for ASAS40 (each probability is imputed based on 20 data sets).
- Analyses using the principal analysis model are aggregated across the 20 imputed data sets using SAS® PROC MI ANALYZE in order to compute a p-value for the treatment comparison for a given value of the response probability.

Sensitivity of the analysis conclusion is determined by gradually increasing the response probability value, thus evaluating scenarios with increasingly imputed response rate for patients treated with placebo. The tipping point is identified as the probability value which leads to a loss of statistical significance when evaluating ixekizumab relative to the placebo group.

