## 6.5. Multiple Comparisons/Multiplicity

A multiple testing strategy for the primary and major secondary objectives will be implemented to control the family-wise type I error rate at a 2-sided  $\alpha$  level of 0.05. The primary outcomes of ASAS40 at Week 16 (for regulatory agencies that accept Week 16 as primary endpoint) and ASAS40 at Week 52 (for regulatory agencies that require Week 52 as primary endpoint) will be tested. These tests will use the primary analysis method, logistic regression analysis with treatment, geographic region, and screening MRI/CRP status in the model, with NRI missing data imputation approach. Because this study has different primary endpoints for different regulatory agencies, the significances of both primary endpoints will not be required in order for the study to be considered successful. No further multiplicity adjustment will be made for the 2 primary endpoints.

Since Study RHBX is conducted to meet registration requirements from various regulatory agencies, 2 separate lists of primary and major secondary outcomes are created and multiplicity adjustment is conducted within each of the lists [each list will be tested at a total alpha of 0.05], using the graphical multiple testing procedure (Bretz et al. 2011). This graphical approach is a closed testing procedure; hence, it strongly controls the family-wise error rate (Alosh et al. 2014).

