### 6.5.1. For regulatory agencies that accept Week 16 endpoints for approval purposes

For regulatory agencies that accept Week 16 endpoints for approval purposes, the following is the list of primary and major secondary outcomes to be tested for both ixekizumab 80 mg Q2W and Q4W regimens at Week 16:

- Primary - proportion of patients achieving an ASAS40 response [ASAS40] at Week 16
- Secondary 1 - change from baseline in ASDAS score [ASDAS CFB] at Week 16
- Secondary 2 - change from baseline in BASDAI [BASDAI CFB] at Week 16
- Secondary 3 - change from baseline in SF-36 PCS [SF-36 PCS CFB] at Week 16
- Secondary 4 - proportion of patients achieving ASDAS low disease activity [ASDAS  $< 2.1$ ] at Week 16
- Secondary 5 - change from baseline in MRI of the SI joint SPARCC score [MRI SPARCC SIJ CFB] at Week 16

The 5 major secondary outcomes are grouped into 2 tiers for testing ([Figure RHBX.6.2](#)).

[figure not shown]
Figure RHBX.6.1 shows the graphical testing scheme with initial  $\alpha$  allocation and weights, and Figure RHBX.6.2 shows the graphical testing schemes used within the Tier 1 and Tier 2 groups of endpoints. All comparisons are at Week 16. The testing steps are outlined below:

The primary outcome of ASAS40 at Week 16 will be initially tested for ixekizumab 80 mg Q2W versus placebo at a 2-sided  $\alpha=0.02$ , and for ixekizumab 80 mg Q4W versus placebo at a 2-sided  $\alpha=0.03$ . If neither null hypothesis can be rejected, no further testing is conducted as the  $\alpha$  for the test of ixekizumab 80 mg Q2W versus placebo and the  $\alpha$  for the test of ixekizumab 80 mg Q4W versus placebo are considered ‘spent’ and cannot be passed to other endpoints.

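### Twenty imputations per scenario leave Monte Carlo noise in the tipping points of SAP 6.3.5; more imputations, a fixed seed and a stated threshold would remove most of it at no real cost

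*SAP*

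**What the plan says.** SAP 6.3.5 plans tipping-point analyses of ASAS40 and of change in ASDAS at Weeks 16 and 52. Observations after ixekizumab rescue are set to missing, and missingness from discontinuation is treated in the same way.

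- **ASDAS.** Monotone dropouts are imputed by Bayesian regression ("using Proc MI with MONOTONE option, 20 imputed data sets"). A delta is added to the imputed scores and the steps are repeated as delta grows. "The tipping point is identified as the delta score value which leads to a loss of statistical significance".
- **ASAS40.** Missing responses are imputed at a set of fixed response probabilities, and "each probability is imputed based on 20 data sets". The example values for placebo are "probability = 0, 0.2, ..., 1, respectively"; those for ixekizumab go up in steps of 0.1, with NRI as the extreme case. "Analyses using the principal analysis model are aggregated across the 20 imputed data sets" to give one p-value per scenario. "The tipping point is identified as the probability value which leads to a loss of statistical significance".

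The visible text of 6.3.5 gives no numeric significance threshold, no seed rule and no check on Monte Carlo error. On alpha, SAP 6.5 says that "each list will be tested at a total alpha of 0.05"; within the Week 16 list (6.5.1), ASAS40 starts at 0.02 for Q2W and 0.03 for Q4W. SAP 6.10.5 classes the tipping-point analysis as a sensitivity analysis, beside placebo multiple imputation (pMI).

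**The concern.** The output of a tipping-point analysis is the place on a grid where a simulated p-value crosses a line. Close to that line a modest change in p alters the answer, so this output needs a more stable p-value than an ordinary multiple-imputation analysis with a result far from the threshold.

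With 20 imputations, both the pooled estimate and its estimated variance carry simulation error. The error grows with the FMI. At Week 52 the FMI could be appreciable, because any patient may be rescued from Week 16 to Week 44 and everything after rescue is set to missing.

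At stake is how firmly the reported tipping point can be quoted. If it partly reflects the random seed, it is a weaker statement of how bad the missing outcomes would have to be before the conclusion changed.

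**Working it through.** **Inputs.** m = 20 (SAP 6.3.5). The documents state no Monte Carlo error, so there is no planned figure to reproduce on this point. The FMI, the rescue rate and the dropout rate are not given either; FMI from 0.05 to 0.4 is an assumption.

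**Model.** Use Rubin's rules on a scale where total variance is 1 with unlimited imputations: between-imputation variance B = FMI, within-imputation variance W = 1 - FMI. With m imputations:

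- the pooled z varies around its limit with variance B/m;
- the estimate of B varies as B × chi-square(m-1)/(m-1);
- T = W + (1 + 1/m)B, and p comes from a t distribution with Rubin's degrees of freedom.

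**Hand check at FMI 0.2, m = 20.**

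- Noise in the estimate: variance 0.2/20 = 0.0100.
- Noise in the variance: SD of estimated B = 0.2 × √(2/19) = 0.065; times 1.05 = 0.068. T is about 0.80 + 0.21 = 1.01, so the standard error varies by 0.068/(2 × 1.01) = 3.4%, which moves z by 1.96 × 0.034 = 0.066.
- Combined SD of z: √(0.0100 + 0.066²) = 0.120.
- z = 1.96 ± 1.96 × 0.120, or 1.72 to 2.20, so p runs from about 0.085 down to 0.028.

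**Simulation of the same model** (at least 200,000 draws per cell). The range columns are 95% ranges of p when the unlimited-m p is 0.05. The last two columns show how often an unlimited-m p of 0.03 appears as p > 0.05.

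| FMI | Range, m = 20 | Range, m = 100 | Range, m = 200 | 0.03 shown as > 0.05, m = 20 | Same, m = 100 |
|---|---|---|---|---|---|
| 0.05 | 0.039-0.064 | 0.045-0.056 | 0.046-0.054 | <0.1% | <0.1% |
| 0.1 | 0.035-0.072 | 0.043-0.059 | 0.045-0.056 | 0.5% | <0.1% |
| 0.2 | 0.029-0.086 | 0.039-0.064 | 0.042-0.059 | 6% | <0.1% |
| 0.4 | 0.020-0.116 | 0.034-0.073 | 0.038-0.066 | 19% | 1% |

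With m = 200 the 19% falls to about 0.04%. If the line were 0.02 instead of 0.05, the m = 20 range at FMI 0.2 would be 0.0105-0.039, so the relative noise is similar.

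**Which FMI is plausible?** As an approximation, let d be the missing share, R² the variance explained by earlier visits, and x = (1 - R²)d/(1 - d). Then FMI = x/(1 + x). FMI 0.4 means x = 0.4/0.6 = 0.667. That needs d = 40% if R² = 0, or d/(1 - d) = 0.667/0.6 = 1.11, so d = 53%, if R² = 0.4. This is conceivable at Week 52. It is unlikely at Week 16, because rescue starts only after the Week 16 assessments (Protocol 6.8.2).

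**Direct simulation of the ASAS40 procedure** (100 per arm, unadjusted log odds ratio, 4,000 repeats, m = 20, at the first 0.01 step of placebo probability where p reaches 0.05):

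- Week 52, assumed missing 20-40% on ixekizumab and 40-60% on placebo: FMI about 0.09-0.28, with p ranges from 0.041-0.078 to 0.025-0.097.
- Week 16, assumed 10% missing per arm, rates 35% vs 20%: FMI 0.05-0.09, p about 0.037-0.069.
- Week 16, planned rates 46% vs 18%, 5-10% missing: no tipping point for ixekizumab response probabilities of 0 to 0.2.

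**Grid spacing.** With 30% vs 15% and 30%/50% missing, the first placebo step, from 0 to 0.2, takes p from 0.012 to 0.47, far more than the noise. Where a grid point lies near the line (0.0425 and 0.0484 in two scenarios), 20 imputations can put it on either side.

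**The case against.** A reader might infer that p generally swings between 0.02 and 0.12. The documents do not support that: it needs an FMI of about 0.4, no rescue or dropout rate is stated, and the direct ASAS40 simulations reached at most about 0.10. For ASDAS, imputation conditions on earlier visits, which lowers the FMI below the missing share. At Week 16 the noise is small.

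A reader might also take 0.05 as the planned cut-off. SAP 6.3.5 says only that significance is lost, and ASAS40 in the Week 16 list starts at 0.02 and 0.03. The 0.05 figures above are illustrations. The missing number is itself part of the point.

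Nor do the documents show that neighbouring grid points would tip and un-tip at random. That assumes fresh draws at each point, and the visible text does not say whether seeds differ. With common draws, a larger delta shifts results systematically. Appendix 2, which 6.3.5 cites for the method's justification, is blacked out and may cover seeds or the choice of m.

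Finally, the consequence is bounded. The primary analysis is logistic regression with NRI and uses no random draws. The NRI extreme of the ASAS40 grid has none either. The tipping-point analysis is one of several supporting analyses, with pMI, categorical MMRM, Fisher's exact test and the per-protocol set.

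All of this limits the size of the point. What remains is that 20 is fixed for both endpoints, the reported result is a threshold crossing, and the noise near the threshold can be removed cheaply.

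**Conclusion.** The point stands as a free improvement. Near the threshold, 20 imputations leave noise that is small at the FMI plausible for Week 16, noticeable at FMI 0.2, and large only if FMI approaches 0.4 at Week 52. All sizes are conditional on the assumed FMI and, where 0.05 is used, on that cut-off. The effect is confined to the reported tipping point: usually about one step on the ASAS40 example grid. No step size is given for the ASDAS delta, so the shift there cannot be expressed in steps. It does not reach the NRI primary analysis or any test under multiplicity control.

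**What to change.** In SAP 6.3.5:

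1. Raise the number of imputations wherever 20 is stated (four places: one for ASDAS, three for ASAS40). 200 is a reasonable choice, not a unique one: 100 already brings the 19% down to about 1%.
2. Use one fixed seed across the grid, so that neighbouring scenarios share draws and the boundary is smooth. If Appendix 2 already says this, a cross-reference is enough.
3. State the significance threshold that defines tipping: 0.05, or the alpha assigned to the comparison under 6.5.
4. Report the Monte Carlo error of p at the grid points around the tipping point.

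The cost is computing time and a few lines of text. Estimand, imputation model and primary test do not change.

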#### **6.4. Multicenter Studies**

This study will be conducted by multiple investigators at multiple sites internationally. The countries will be categorized into geographic regions, as described in Section 6.2, for analysis.

For the analysis of the primary endpoint, the presence of a treatment-by-geographic region interaction will be tested at 10% significance level. Treatment group comparisons for the

primary outcome will be presented separately for each geographic region. When there is evidence of an interaction ( $p < .10$ ), descriptive statistics may be used to assess whether the interaction is quantitative (that is, the treatment effect is consistent in direction but not size of effect) or qualitative (the treatment is beneficial for some but not other geographic regions or countries).

